7.4.4 Pharmacokinetic Assessment

The PK of MEDI-551 will be estimated by non-compartmental analysis. A population PK analysis may also be performed to obtain additional PK parameters. Those PK parameters will be summarized by descriptive statistics including N, mean, standard deviation, coefficient of variation, median, minimum, maximum, and geometric mean.

7.4.5 Assessment of Effect on Circulating Lymphocyte Populations

Circulating levels of blood mononuclear cells, including T-cells, B-cells, NK cells and monocytes will be determined using standard clinically available flow cytometry. B-cell levels will be monitored from start of treatment until recovery or study discontinuation due to initiation of alternative anticancer therapy or subject withdrawal. Recovery will be defined as a B-cell count of ≥ 200 cells/ μ L in subjects with baseline B-cells of ≥ 200 cells/ μ L or two

consecutive B-cell counts within $\pm 20\%$ of baseline in subjects with baseline B-cell counts of < 200 cells/ μL . Time to B-cell recovery will be analyzed. The correlation between Ig levels and B cell counts during treatment and recovery will also be evaluated.

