D) was added to this study to evaluate the clinical activity of MEDI-551 monotherapy in subjects with any anti-CD20-refractory aggressive lymphoma. The rationale for this arm was based on data from Arm A, demonstrating the activity of single-agent MEDI-551 in a heavily pretreated relapsed refractory patient population that had received prior rituximab. Detailed justification for these study arms is provided below.

Rationale for Arm B

Clinical and PK data from Arm A of the Phase 1/2 study suggest that the lack of full exposure in CLL subjects compared with FL and DLBCL subjects may have resulted in reduced clinical activity in CLL (response: 19% CLL [n = 26] vs 29% FL [n = 34] and 23% DLBCL [n = 26]). The number of circulating malignant B cells is much higher in CLL patients than in those with other B-cell malignancies. Therefore, to maximize tumor cell killing, the dose of antibody should be sufficient to saturate the B-cell antigens (B-cell sink). Subjects with CLL treated with MEDI-551 at the 12-mg/kg dose demonstrate lower plasma concentrations of MEDI-551 than other subjects treated at that dose (mean minimum observed concentration at steady state is 89.5 ± 45.7 $\mu\text{g/mL}$ for CLL and 134 ± 40.6 $\mu\text{g/mL}$ for non-CLL), suggesting that the B-cell sink may not be saturated at the 12-mg/kg dose. Moreover, studies of rituximab have reported markedly lower rituximab concentrations/exposure and a low response rate (13%) in patients with SLL or CLL compared to patients with FL (60%) treated at the same dose of 375 mg/m^2 weekly for 4 weeks ([McLaughlin et al, 1998](#)). A greater response rate (50%) was seen in CLL patients given rituximab at 375 mg/m^2 three times weekly for 4 weeks ([Byrd et al, 2001](#)), suggesting that dose intensity established via frequent dosing may also improve response rates. Additionally, dose intensity with higher doses of the MAb may be effective in improving responses as suggested by a response rate of 75% in patients receiving a rituximab dose of 2250 mg/m^2 weekly for 4 weeks ([O'Brien et al, 2001](#)). These data suggest that higher response rates with MEDI-551 may be achieved with increased dose density by using higher doses and/or more frequent dosing. Therefore, additional dose escalation with MEDI-551 was warranted in CLL subjects to determine the MTD or the effective dose that may overcome the B-cell sink.

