2.2 Secondary Objectives

The secondary objectives of this study are listed by study arm.

Arm A

1. To determine the preliminary efficacy profile of MEDI-551 in subjects with advanced B-cell malignancies (CLL [including SLL], DLBCL, and FL)
2. To determine the PK of MEDI-551 in subjects with advanced B-cell malignancies
3. To determine the effect of treatment with MEDI-551 on circulating lymphocyte populations and Ig levels, including time to recovery after treatment
4. To determine the IM of MEDI-551 in subjects with advanced B-cell malignancies

Arm B

1. To evaluate the PK and IM of MEDI-551 at doses studied in subjects with relapsed or rituximab-refractory CLL
2. To evaluate the effect of therapy on the B-lymphocyte level in peripheral blood, including time to recovery of B-lymphocyte level

Arm C

1. To evaluate the PK and IM of MEDI-551 when administered in combination with rituximab in subjects with aggressive lymphomas
2. To evaluate the effect of therapy on the B-lymphocyte level in peripheral blood, including time to recovery of B-lymphocyte level

Arm D

1. To determine the safety and tolerability of MEDI-551 in subjects with any anti-CD20-refractory aggressive lymphomas
2. To evaluate the PK and IM of MEDI-551
3. To evaluate the effect of therapy on the B-lymphocyte level in peripheral blood, including time to recovery of B-lymphocyte level

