7.3.2 Secondary Endpoints

Arm A

1. Clinical activity/efficacy: CR, duration of CR, PR, objective response, disease control, TTR, duration of objective response, duration of disease control, PFS, and OS
1. Effect of MEDI-551 on circulating lymphocyte populations: circulating levels of blood mononuclear cells, including T-cells, B-cells, NK cells and monocytes
2. Pharmacokinetics: PK profiles and parameters, including maximum observed concentration (C_{max}), AUC, clearance (CL), and $t_{1/2}$, of MEDI-551
3. Incidence of anti-MEDI-551 antibodies based on samples obtained from each subject at multiple timepoints before and after dosing

Arms B and C

1. Pharmacokinetics: PK profiles and parameters, including C_{max} , AUC, CL, and $t_{1/2}$, of MEDI-551
1. Incidence of anti-MEDI-551 antibodies based on samples obtained from each subject at multiple timepoints before and after dosing
2. Effect of MEDI-551 on B-lymphocyte levels in peripheral blood, including time to recovery of B-lymphocyte level

Arm D

1. Safety: AEs, SAEs, laboratory evaluations, vital signs, physical examinations, and ECGs
2. Pharmacokinetics: PK profiles and parameters, including C_{max} , AUC, CL, and $t_{1/2}$, of MEDI-551
3. Incidence of anti-MEDI-551 antibodies based on samples obtained from each subject at multiple timepoints before and after dosing
4. Effect of MEDI-551 on B-lymphocyte levels in peripheral blood, including time to recovery of B-lymphocyte level

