 - Additional safety assessments that have not been informative during later cycles of MEDI-551 will not be required at each cycle (note these evaluations are retained at EOT). This includes (when applicable) ECG, coagulation, urinalysis; liver function will continue to be evaluated at each cycle), PK, ADA, and B-cell monitoring (B-cell levels in non-CLL subjects were generally very low at baseline, likely due to prior anti-cancer treatments. B-cell levels in CLL subjects were often elevated at baseline; however, this is likely reflects malignant rather than normal B cells. Across populations, B cells were nearly or fully depleted following > 6 cycles).
 - Exploratory evaluations are removed.
 - Disease evaluations will be performed at regular intervals to determine whether MEDI-551 is continuing to provide clinical benefit.
 - Subjects with DLBCL, FL, MCL, or transformed indolent lymphoma who have completed > 1 year of treatment: disease evaluation is required once every 6 months.

- Subjects with CLL who have completed > 1 year of treatment: after which CT scans for disease evaluation are only required once every 6 months if clinically indicated (eg previous indication to treat was based on predominantly nodal disease) or if indicated based on hematology findings.
- At the EOT Visit, all safety assessments will be performed, but exploratory evaluations are removed. Evaluations used to confirm CR are removed (where applicable).
- Safety follow-up will be conducted at the 90-Day Post Last Dose Visit (also known as End of Study). All safety assessments will be performed; exploratory evaluations are removed. The 30 Days post-EOT visit is removed.
- Long-term follow-up for progression-free survival and overall survival will be discontinued once Version 13.0 is in effect. All subjects who have completed treatment and safety follow-up through at least the 90-Day Post Last Dose Visit (ie approximately 90 days post last dose), withdrawn consent, or been lost to follow-up will be considered to have completed the study.

Major changes to the protocol are described below.

1. Title Page: The Medical Monitor was changed from [name] to [name] [name] as the primary medical monitor. [name] title and contact information were updated.
2. [name] was added as the secondary medical monitor.
3. Study Abstract:
 - a. The abstract was modified to mirror the changes made to the protocol body.
 - b. Subject numbers were updated to reflect actual enrollment

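### Section 7.4.5 defines B-cell recovery on the total B-cell count in every disease, so in CLL residual or returning leukaemia can be scored as recovery from drug effect

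*Protocol*

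**What the plan says.** Section 7.4.5 obtains the B-cell level from a total count, which "will be determined using standard clinically available flow cytometry". It then fixes a two-branch rule.

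- Baseline of 200 cells/µL or more: "Recovery will be defined as a B-cell count of" at least 200 cells/µL. One count is enough.
- Baseline below 200 cells/µL: two consecutive counts within 20% of baseline in either direction.

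The section makes no exception for any disease. It does not separate clonal from normal B cells and does not require that a subject was first depleted. It adds that time to recovery will be analysed and that the correlation of immunoglobulin levels with B-cell counts will be examined during treatment and recovery. On follow-up it says: "B-cell levels will be monitored from start of treatment until recovery or study discontinuation due to initiation of alternative anticancer therapy or subject withdrawal".

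Time to recovery belongs to a secondary objective in every arm. In Section 2.2, Arm A (which includes CLL) couples it with lymphocyte populations and immunoglobulin levels. For Arm B (entirely CLL) the objective reads: "To evaluate the effect of therapy on the B-lymphocyte level in peripheral blood, including time to recovery of B-lymphocyte level". Section 7.3.2 repeats this as an Arm B endpoint.

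Two other places describe what is being counted in CLL. Section 1.5, in the rationale for Arm B, says: "The number of circulating malignant B cells is much higher in CLL patients than in those with other B-cell malignancies". The Version 13.0 rationale in Section 15 says: "B-cell levels in CLL subjects were often elevated at baseline; however, this is likely reflects malignant rather than normal B cells".

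**The concern.** A recovery time is normally read as how long a drug keeps B cells suppressed before the normal compartment returns. Pairing it with immunoglobulin levels, as Section 7.4.5 does, invites that reading. In CLL the total count cannot carry it: a rise through 200 cells/µL may be normal reconstitution, regrowth of the clone, or leukaemia that was never cleared, and the rule treats all three alike.

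What is at stake is the meaning of a stated secondary endpoint in Arm B and in the CLL part of Arm A. If Arm A is summarised as a whole, one recovery curve would combine events of different kinds from CLL and lymphoma subjects. The immunoglobulin correlation is affected too, because leukaemic cells in the recovery phase do not represent restored humoral immunity.

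**Working it through.** No power, sample size or event count is attached to this endpoint, so there is no plan figure to reproduce. The check applies the rule to the protocol's own description of CLL and then counts the subjects who could be affected.

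**Step 1. Which branch applies.** Section 15 (Version 13.0) describes baseline B cells as generally very low in non-CLL subjects and often elevated in CLL. The branch for baselines of 200 or more is therefore the one many CLL subjects can be expected to enter. It has no upper limit, no confirmation and no prior-depletion condition.

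**Step 2. What that branch does.** The counts below, in cells/µL, are assumed for illustration and are not from the protocol. Baseline is 20,000 throughout.

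| Course | Count | Share of baseline | Scored as |
|---|---|---|---|
| Nadir 50, clone regrows | 250 | 250 / 20,000 = 1.25% | recovered |
| Nadir 50, count at progression | 50,000 | 50,000 / 20,000 = 250% | recovered |
| Partial fall only, never below 200 | 2,000 | 2,000 / 20,000 = 10% | recovered at the first post-baseline count |

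In the third course the subject has a recovery time without having been depleted.

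**Step 3. Whether such counts can be sampled.** Documented progression ends dosing (Section 6.4.1). Under Version 13.0, flow cytometry is scheduled at the end-of-treatment visit and the 90-day visit (Table 5.2.1-1). An end-of-treatment sample prompted by progression can therefore be the one that meets the rule. CLL response is also assessed through haematology (Section 5.3.6), so one rise in blood counts can bear on both progression and recovery.

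**Step 4. Subjects exposed.**

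- CLL in Arm A: 26 (Sections 1.5 and 3.1). Arm B: 7 (Section 7.5). Sum: 26 + 7 = 33.
- Enrolled: Arm A 26 + 69 = 95; then 95 + 7 + 19 + 16 = 137.
- Share: 33 / 137 = 24%.

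This is a ceiling. Baselines are described only as often elevated, and the CLL group includes SLL. Subjects starting below 200 fall under the 20% rule, where an overshoot beyond 20% above baseline is not recovery. The protocol does not give the number with a baseline of 200 or more.

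**The case against.** The best defence is that the endpoint is worded as the B-lymphocyte level in blood, not as normal B cells or immune reconstitution. MEDI-551 targets CD19 on malignant and normal B cells alike, and Arm B was built to saturate a sink that the protocol ties to circulating malignant cells. Return of the total count is then a coherent sign that suppression has ended. This stands in part: a total-count measure is worth reporting in CLL. It does not rescue the label of recovery, the scoring of subjects who were never depleted, or the immunoglobulin correlation.

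Several stronger readings are tempting but unsupported.

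- A reader might infer that every recovery event in Arm B is uninterpretable. Some subjects may start below 200, and some returning cells may be normal.
- A reader might infer that subjects with the poorest disease control will recover fastest. The protocol gives no regrowth data, and Section 15 reports near or full depletion across populations after more than six cycles, although that speaks only for subjects treated that long.
- A reader might infer open-ended sampling after progression because Section 7.4.5 does not name it as an end to monitoring. Section 6.4.1 shows that before Version 13.0 follow-up after progression was for survival only, and Version 13.0 confines flow cytometry to two visits.

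It can also be said that analysis detail belongs to the statistical analysis plan and that one supporting sentence sits in an amendment summary. The definition itself, however, is fixed in the protocol. The sentence explains the current version rather than superseded text, and Section 1.5 supports the point independently. Section 7.1 summarises by treatment group, which keeps Arm B apart from the lymphoma arms but does not separate CLL from lymphoma within Arm A.

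**Conclusion.** The point holds as a flaw in a stated definition. For CLL subjects with a baseline of 200 cells/µL or more, the rule in Section 7.4.5 scores residual or returning leukaemia as recovery, contrary to the protocol's own account of those cells. At most about 33 of 137 subjects (24%) are exposed. The true number depends on baseline counts, and the shift in recovery times depends on regrowth timing; the protocol gives neither, so the bias cannot be quantified.

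The conclusion rests on reading Section 7.4.5 as written; an unseen analysis plan might narrow it. The reach is limited to a descriptive secondary pharmacodynamic endpoint and its immunoglobulin correlation. No primary endpoint, hypothesis or sample size is touched.

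**What to change.** Amend Section 7.4.5 as follows.

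1. Analyse time to B-cell recovery, and the immunoglobulin correlation during recovery, as recovery in non-CLL subjects only. Do not pool CLL with non-CLL subjects in Arm A.
2. For CLL (Arm A CLL and Arm B), report total B-cell counts over time, and time to return to at least 200 cells/µL among subjects first documented below 200. Label both as including malignant cells and as not describing immune recovery. Simply renaming the measure duration of depletion would not help, since depletion ends on the same total count.
3. Align the Arm A and Arm B wording in Sections 2.2 and 7.3.2, and the abstract that repeats it.

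Censoring at progression in all arms is not recommended. In CLL it would be informative, because progression and B-cell return are linked; in lymphoma no contamination of the count has been shown. At most, mark progression on the CLL displays or add a sensitivity analysis.

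The cost is a few sentences, a disease flag in the analysis and no new samples. The loss is a normal B-cell recovery estimate in CLL, which the total count cannot supply in any case.

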Since the safety and tolerability of the 12-mg/kg dose of MEDI-551 has been verified in Arm A, approximately 26 subjects with any anti-CD20-refractory disease were to be enrolled and treated with single-agent MEDI-551 at the dose and schedule used in the expansion cohort of Arm A (ie, 12 mg/kg of MEDI-551 on Days 1 and 8 of Cycle 1, and on Day 1 of Cycle 2 and beyond in 28-day cycles). A total of 16 subjects were enrolled in Arm D. Treatment may continue until the subject experiences unacceptable toxicity, disease

progression, withdraws consent, or achieves a CR (2 additional cycles of MEDI-551 at the same dose may be administered before EOT).

[figure not shown]

Figure 3.1-4 Flow Diagram for Treatment in Arm D

The endpoints to be measured in this study are described in Section 7.3.

3.2 **Estimated Study Duration**

The duration of investigational product treatment will be determined by disease response and safety. Safety follow-up assessments will be conducted through approximately 90 days after the last dose of investigational product, which is equivalent to approximately 60 days post-EOT Visit. The estimated study duration is approximately 8 to 10 years from the time the first subject is enrolled in the study. Study completion is defined as the date of the last protocol-specified visit for the last subject in the study.

4 **STUDY PROCEDURES**

4.1 **Subject Participation and Identification**

Study participation begins once written informed consent is obtained (see Section 10.3 for details). Once informed consent is obtained, a subject identification (SID) number will be assigned by a central system (eg, an interactive voice response system [IVRS]), and the screening evaluations may begin to assess study eligibility (inclusion/exclusion) criteria. The

SID number will be used to identify the subject during the screening process and throughout study participation, if applicable.

A master log will be maintained of all consented subjects and will document all screening failures (ie, subjects who are consented but do not meet study eligibility criteria).

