- **Progression-free survival:** Progression-free survival will be measured from start of MEDI-551 administration until the first documentation of PD/relapse or death, whichever occurs first. Progression-free survival will be censored on the date of last disease assessment for subjects who have no documented PD/relapse or death prior to data cutoff, dropout, or the initiation of alternative anticancer therapy.
- **Overall survival:** Overall survival will be determined as the time from the start of MEDI-551 administration until death. For subjects who are alive at the end of study or lost to follow-up, OS will be censored on the last date when subjects are known to be alive.

The analysis methods will differ by the types of endpoints. For categorical endpoints, proportions will be summarized, 80% and 95% confidence intervals will be calculated using the Clopper-Pearson exact method. For time-to-event endpoints, Kaplan-Meier method will be used to describe the endpoints graphically and to estimate the median or the event rates at time of interest.

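### The B-cell recovery rule in Section 7.4.5 has an upper limit for baselines below 200 cells/µL, so a subject whose counts rise past 1.2 times baseline and stay there is never scored as recovered (minor)

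*Protocol*

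**What the plan says.** Section 7.4.5 of the Protocol gives two definitions of B-cell recovery, split at a baseline of 200 cells/µL.

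- Baseline of 200/µL or more: "Recovery will be defined as a B-cell count of" at least 200/µL. One count is enough.
- Baseline below 200/µL: two "consecutive B-cell counts within $\pm 20\%$ of baseline in subjects with baseline B-cell counts of" less than 200/µL.

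The same section says that "B-cell levels will be monitored from start of treatment until recovery" or until the subject leaves the study, and that time to recovery will be analysed. It gives no further condition on which counts qualify.

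Time to recovery belongs to a secondary objective in every arm. Section 2.2 words it for Arm A as "To determine the effect of treatment with MEDI-551 on circulating lymphocyte populations and Ig levels, including time to recovery after treatment", and for Arms B, C and D as "To evaluate the effect of therapy on the B-lymphocyte level in peripheral blood, including time to recovery of B-lymphocyte level". Section 7.3.2 lists it as a secondary endpoint in Arms B, C and D: "Effect of MEDI-551 on B-lymphocyte levels in peripheral blood, including time to recovery of B-lymphocyte level". The Arm A list there names circulating cell levels but not time to recovery.

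**The concern.** Recovery is a return to at least some level, so more B cells should never make a subject less recovered. The low-baseline branch breaks this. Its two-sided band treats a count above 1.2 times baseline in the same way as a count below 0.8 times.

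This is the branch in which overshoot is easy to imagine. The Version 13.0 summary in Section 15 reports that B-cell levels in non-CLL subjects were generally very low at baseline and attributes this to earlier anticancer treatment. A subject who starts from a treatment-suppressed level may later rise well above it, and the band around a very low baseline is only a few cells wide. Such subjects would be carried as not recovered, and the time-to-recovery summary would be wrong for them.

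The high-baseline branch raises a lesser question. It asks for one count of at least 200/µL and does not state that the count must come after a fall. CLL subjects, whose baselines Section 15 describes as often elevated, are the ones for whom this matters.

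**Working it through.** The Protocol gives no sample size, rate or other figure for this endpoint, so there is nothing to reproduce. The check applies the written rule to numbers.

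**The band.** For baseline b below 200/µL, a qualifying count lies between 0.8b and 1.2b. The width is 0.4b and the ratio of the limits is 1.2/0.8 = 1.5.

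| Baseline (/µL) | Band (/µL) |
|---|---|
| 10 | 8 to 12 |
| 50 | 40 to 60 |
| 100 | 80 to 120 |
| 150 | 120 to 180 |
| 190 | 152 to 228 |

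**Clash with the other branch.** A count of 200/µL is above the band when 1.2b < 200, that is when b < 200/1.2 = 166.7/µL.

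**Illustrative series under the written rule and under a floor only** (two consecutive counts of at least 0.8b):

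- b = 100, counts 0, 0, 0, 60, 150, 180, 200. Written rule: never recovered. Floor only (80): recovered at the sixth count.
- b = 150, counts 0, 0, 250, 260, 240. Written rule: never recovered, although every late count is above 200. Floor only (120): recovered at the fourth count.
- b = 100, counts 0, 0, 0, 60, 95, 105. Recovered at the sixth count under both.

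So a slow climb through the band is scored correctly and a steep one is missed.

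**Agreement between branches after the change.** For b < 200, the floor 0.8b is below 160, so two consecutive counts of 200/µL or more always qualify.

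**Measurement variation (illustration).** Assume lognormal counts, independent between visits, with a within-subject CV of 10, 20, 30 or 40%; the Protocol gives no CV. For a subject whose true level has settled at 1.5 times baseline, the chance that a given pair of consecutive counts qualifies is:

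- written rule: 0.0002, 0.017, 0.043, 0.053;
- floor only: 1.00, 0.999, 0.97, 0.90.

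**Size of the branch.** Enrolment was 95 + 7 + 19 + 16 = 137 (Section 15, Version 13.0). CLL subjects number about 26 in Arm A (the count used for the PK evaluation in Section 3.1, not an enrolment total) and 7 in Arm B, giving 33. That leaves about 137 − 33 = 104 non-CLL subjects. This is roughly the group in which low baselines are expected, not a count of subjects affected.

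**High-baseline branch, read literally.** Baseline 300 with counts 250, 0, 0, 0, 0 is recovered at the first count. An illustrative baseline of 50,000 with a first count of 400 is also recovered at that count, after a fall of 1 − 400/50,000 = 99.2%.

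**The case against.** The two-sided band cannot be argued away, because the Protocol fixes it and no other section removes the ceiling. The strongest objections concern how much else can be built on it.

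*The high-baseline branch.* A reader might infer that early CLL counts will be recorded as recoveries. That needs an uncharitable reading. Recovery presupposes a fall, the closing sentence of Section 7.4.5 treats treatment and recovery as separate phases, and the Arm A objective places recovery after treatment. The monitoring sentence describes a sampling window and does not make every count in it eligible. Section 15 also reports near or full depletion after more than 6 cycles, which confines the question to earlier samples. What stands is a gap in wording.

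*Direction of bias.* A reader might infer that Kaplan-Meier times will be too long in one branch and too short in the other. The sentence "For time-to-event endpoints, Kaplan-Meier method will be used to describe the endpoints graphically" stands in Section 7.4.3, on efficacy; Section 7.4.5 names no method.

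*A miss rate.* One could assume exponential regrowth with doubling time D and sampling interval T. Time in the band is then D × log2(1.5) = 0.585D, and two in-band counts are impossible when D < T/0.585 = 1.71T. This needs growth that continues past the band. A subject who levels off near baseline can be caught whatever the doubling time, and the earlier B-cell schedule is not in this version. No rate of misclassification follows.

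*What belongs in the SAP.* Section 7.1 leaves details of endpoint analysis to the SAP. Time origin, depletion threshold and display by disease fall there, and their absence is not a fault. The recovery definition is different because Section 7.4.5 states it.

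**Conclusion.** The point holds for the low-baseline branch on the wording alone, without any assumption about growth, variability or visit spacing. The ceiling at 1.2 times baseline leaves a subject who rises past it without two consecutive in-band counts, and stays above, permanently unrecovered; one who later settles into the band is scored late. For baselines below 166.7/µL, the two branches disagree about a count of 200/µL. The branch applies to many subjects, given the very low non-CLL baselines reported, but the number misclassified cannot be derived from the Protocol.

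The missing depletion condition in the high-baseline branch is a clarification, not a second fault of equal weight.

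The effect is limited to one secondary pharmacodynamic endpoint. Determination of the MTD, the safety summaries and the response analyses do not use it. The severity is minor.

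**What to change.** In Section 7.4.5, for baselines below 200/µL, replace the ±20% band with two consecutive counts of at least 80% of baseline and no upper limit.

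For baselines of 200/µL or more, add that only counts after documented B-cell depletion qualify, in line with the Arm A objective. Leave the depletion threshold, the time origin and any display by disease to the SAP. The threshold needs some care: a single count below 200/µL would be a weak test near the cut-off. At an unchanged true level of 210/µL and an assumed CV of 20% (lognormal), z = ln(200/210)/√ln(1.04) = −0.0488/0.198 = −0.246, so about 40% of single counts would fall below 200 by variation alone.

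The cost is definition text and derivation code, with no new sampling. One small downside is that, without the ceiling, a rise due to malignant B cells in a low-baseline subject would count as recovery, as it already does in the high-baseline branch. The two-count requirement stays as it is now. Under Table 5.2.1-1, B cells are sampled only at the EOT and 90-day visits, so from Version 13.0 on only those two samples can add to a subject's series.

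### Below 200 cells/µL, the recovery rule in Section 7.4.5 sets no baseline floor and needs no prior fall, so a subject already depleted at entry can be scored as recovered by staying depleted

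*Protocol*

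**What the plan says.** Section 7.4.5 of the protocol uses two recovery rules, split at a baseline of 200 cells/µL.

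- Baseline of 200 or more: "Recovery will be defined as a B-cell count of" at least 200 cells/µL, an absolute threshold.
- Baseline under 200: two consecutive counts within ±20% "of baseline in subjects with baseline B-cell counts of" less than 200 cells/µL, a threshold relative to the subject's own starting value.

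On timing, the section says "B-cell levels will be monitored from start of treatment until recovery or study discontinuation" for new anticancer therapy or withdrawal. It adds "Time to B-cell recovery will be analyzed", without restricting the analysis to counts taken after dosing has ended. For Arms B, C and D, Section 7.3.2 lists as a secondary endpoint "Effect of MEDI-551 on B-lymphocyte levels in peripheral blood, including time to recovery of B-lymphocyte level". For Arm A, the secondary objective in Section 2.2 covers lymphocyte populations and immunoglobulin levels, "including time to recovery after treatment".

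The Version 13.0 entry in Section 15 explains why B-cell monitoring was reduced. It reports that "B-cell levels in non-CLL subjects were generally very low at baseline, likely due to prior anti-cancer treatments", and that across populations "B cells were nearly or fully depleted following" more than 6 cycles. This is used here as the sponsor's report of observed data, not as superseded protocol text.

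**The concern.** A recovery time has meaning only if there was a level to lose and regain. The rule for baselines under 200 cells/µL assumes that the baseline is such a level. For many non-CLL subjects the protocol says otherwise: prior therapy had already removed most of their B cells. Measured against a depleted baseline, continued depletion looks like a return to baseline.

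The low baselines follow from the design. Sections 4.2.1 and 4.2.2 require prior rituximab in the lymphoma subjects of Arms A and C and prior anti-CD20 therapy in Arm D, while the required gap before the first MEDI-551 dose is never longer than 28 days. The rituximab label in Appendix 2 (section 12.2) reports depletion lasting up to 6 to 9 months in 83% of 166 NHL patients.

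At stake is the description of how long MEDI-551 keeps B cells down. Each false on-treatment recovery is an early event and makes depletion look shorter than it was. The effect would be greatest in Arms C and D, which are entirely aggressive lymphoma.

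**Working it through.** The plan gives no figure to reproduce here, so the check applies the stated rule directly.

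**Step 1: the recovery band.** For baseline b under 200 cells/µL, the band runs from 0.8b to 1.2b.

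| Baseline b | Band (cells/µL) | Is a count of 0 inside? |
|---|---|---|
| 0 | 0 to 0 | yes |
| 1 | 0.8 to 1.2 | no |
| 5 | 4 to 6 | no |
| 10 | 8 to 12 | no |
| 20 | 16 to 24 | no |

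For any b above 0, 0.8b is also above 0, so a count of 0 lies outside the band. A fully depleted count of 0 therefore meets the rule only when b = 0, and then two post-dose zeros are enough. The same can happen when baseline and on-drug results are both at or below the assay limit and are recorded as the same value.

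**Step 2: low but non-zero baselines.** The MEDI-551 sections give no numeric depletion threshold. As an assumption, take the two levels in the appended rituximab label (section 12.2): 10 cells/µL (GPA/MPA) and 20 cells/µL (RA). The whole band lies below 10 when b < 10/1.2 = 8.3, and below 20 when b < 20/1.2 = 16.7. In those ranges, any recovery the rule can score is scored at a depleted count.

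**Step 3: how readily a flat, depleted count is scored.** This is an illustration only. Suppose the true level never changes and both baseline and later counts vary around it (lognormal). The simulated chance of two consecutive in-band counts is:

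| Assumed count CV | 2 post-dose counts | 6 post-dose counts |
|---|---|---|
| 10% | 74% | 95% |
| 20% | 31% | 69% |
| 30% | 16% | 47% |
| 50% | 7% | 24% |

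The documents give neither the CV nor the full sampling schedule. Table 5.2.1-1 shows flow cytometry only at the EOT and 90-day visits; the earlier schedules, which covered most subjects, are no longer in the protocol.

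**Step 4: upper limit on the number exposed.** Enrolment was 95 (Arm A) + 7 (B) + 19 (C) + 16 (D) = 137. Removing the 26 Arm A CLL subjects given in Section 1.5 and the 7 in Arm B leaves 137 − 26 − 7 = 104. Section 1.5 accounts for 26 + 34 + 26 = 86 Arm A subjects with CLL, FL or DLBCL, so the 104 includes 95 − 86 = 9 others, apparently myeloma.

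**Step 5: the other edge of the same band.** From b = 10, a true return to 150 cells/µL lies outside 8 to 12 and is not scored as recovery. A count of 200 falls inside the band only for baselines of about 167 to 199 (200/1.2 = 166.7).

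**The case against.** The strongest reply has four parts.

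1. *The failure is narrow.* A reader might infer that any non-CLL subject depleted by prior therapy can be scored as recovered while fully depleted, or that the rule forces a recovery time on every such subject. The documents do not support either reading. By Step 1, a count of 0 is correctly not recovery for any non-zero baseline, and a subject who never enters the band has no recovery event. Section 15 says baselines were very low, not zero, and reports no subject at 0. This part stands and sets the scope of the point.

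2. *The size is unknown.* The 104 is every non-CLL subject, not those at or near zero. The probabilities depend on assumed variability and sampling. This also stands.

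3. *The SAP may deal with it.* Section 7.1 leaves details of endpoint analyses to the SAP, and handling of values below quantification commonly belongs there. That does not remove the point, because the recovery definition is fixed in the protocol and gives a wrong answer when followed as written. The Arm A objective refers to recovery after treatment, but Section 7.4.5 does not carry that limit.

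4. *Little depends on it.* No hypothesis test, power statement, dose decision or stopping rule uses this endpoint, and Section 15 itself warns readers about low baselines. This stands and keeps the point minor.

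**Conclusion.** The point holds in limited form. For baselines under 200 cells/µL, the rule in Section 7.4.5 can score persistent depletion as recovery during treatment. It does so with certainty when baseline and post-dose counts are all 0, and possibly when on-drug counts stay near a very low baseline. It does not do so when a low non-zero baseline falls to 0.

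The conclusion rests on the wording of the rule and on the sponsor's own report of low non-CLL baselines. It does not rest on the illustrative probabilities. The number affected cannot be stated: about 104 is an upper limit, and the documents give no baseline distribution, count variability or full sampling schedule. Subjects with a baseline of 200 or more are unaffected. This is a minor point on a descriptive secondary endpoint.

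**What to change.** In Section 7.4.5, restrict the analysis of time to B-cell recovery to subjects who have both:

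- a baseline above a pre-stated floor, for example the flow assay's lower limit of quantification, set so that the lower edge of the recovery band can itself be measured; and
- a documented on-treatment fall below that band.

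Report the remaining subjects by arm as *depleted at baseline, not evaluable for recovery*, giving their number and a descriptive summary of their counts over time. Subjects above the floor with no documented fall should be counted separately.

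In the same edit, correct the +20% upper limit so that a true rise above baseline is not excluded. Removing the upper limit alone would not solve the present problem, because 80% of 0 is still 0.

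The cost is one or two sentences and no new data. The downside is that fewer subjects contribute to the recovery estimate, possibly far fewer in Arms C and D; reporting the excluded numbers by arm makes that loss visible.
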